5.5 Identity of Investigational Product

ADC Therapeutics will provide and distribute adequate supplies of ADCT-402 to the study sites. The following drug supplies will be used in the study:

Product	Supplied As
ADCT-402	10-mL single-use, glass vial at a deliverable volume of 3.2 mL (with an
	additional 0.3 mL overfill) at 5 mg/mL (equivalent to 16 mg ADCT-402)

5.5.1 ADCT-402 Drug Product

ADCT-402 is a sterile formulation containing PBD-conjugated RB4v1.2 (DAR ≥1), RB4v1.2 (DAR = 0), and SG3249. It is provided pre-formulated in 10-mL single-use, glass vials containing approximately 16 mg ADCT-402 per vial (deliverable volume 3.2 mL, with an additional 0.3 mL overfill, at 5 mg/mL).

Date of Protocol: 19 April 2017 Page 46 Protocol Amendment 3

ADCT-402-102 Protocol Amendment 3

5.6 Management of Clinical Supplies

5.6.1 Study Drug Packaging and Storage

ADCT-402 will be supplied in a labeled 10-mL stoppered glass vial and shipped to the investigational site. Once the package arrives, the receiving site pharmacy will complete the enclosed forms to acknowledge receipt.

All study drugs must be stored in a secure area (e.g., a locked cabinet). ADCT-402 should be protected from light and stored frozen (-65°C or below). ADCT-402 should be thawed under ambient conditions.

5.6.2 Study Drug Preparation and Administration

After the vials have been completely thawed, they should be gently mixed by swirling to ensure homogeneity and visually inspected before use. The appropriate quantity of ADCT-402 will be removed from the vial with a syringe and diluted into a 50 mL IV bag containing 5% dextrose in water (D5W). The amount of the product to be diluted will depend on the dose level and the body mass of the patient. Once the ADCT-402 has been transferred, the bag should be mixed to ensure homogeneity of the dosing solution. The contents of the IV bag will then be administered to the patient with a dosing pump per institutional guidelines for intravenous fluid (IVF) administration.

Additional instructions regarding study drug handling, storage, and preparation are included in the pharmacy manual.

5.6.3 Study Drug Accountability

The Investigator will maintain accurate records of receipt of all study drugs, including dates of receipt. In addition, accurate records will be kept regarding when and how much study drug is dispensed and used by each patient in the study. Reasons for departure from the expected dispensing regimen must also be recorded. All study drugs will be reconciled and retained or destroyed according to applicable regulations.

5.7 Overdose Management

An overdose is any dose of study treatment given to a patient that exceeds the dose described in the protocol. Any overdose, with or without associated AEs, must be promptly reported to the Sponsor. There are no data available to determine what effects and whether effects of an overdose can be reversed. Symptomatic treatment and standard supportive care measures for the management of this toxicity should be applied.

5.8 Treatment Compliance

Administration of the study treatments will be performed by the Investigator or a qualified designee; therefore, compliance will be verified by the study drug administration information.

ADCT-402-102 Protocol Amendment 3

5.9 Concomitant Treatment

All medications used within 14 days prior to the Day 1 visit and during the treatment period are to be recorded in the eCRF. Concomitant medication information will be collected for 30 days following the patient's last dose of ADCT-402. This will include all prescription drugs, herbal products, vitamins, minerals, and over-the-counter medications. Any changes in concomitant medications will also be recorded in the patient's eCRF.

5.9.1 Prohibited During Study

- Other anti-cancer therapy, with the exception of hormonal therapy for maintenance treatment of breast and prostate cancer.
- Hydroxyurea is not permitted after Cycle 1 unless approved by the Sponsor.
- Other investigational agents.
- Chronic treatment with corticosteroids (prednisone ≥12.5 mg/day or dexamethasone ≥2 mg/day, excluding inhaled steroids).
- Live vaccines.

5.9.2 Permitted During Study

After confirmation and documentation of eligibility, supportive care treatments (transfusions, etc.) can be prescribed as medically appropriate. Hematopoietic growth factors are permitted as per the American Society of Clinical Oncology guidelines (Smith, 2006); however, prophylactic use of growth factors is not allowed during the first treatment cycle.

Patients with a WBC value >15,000 cells/ μ L may receive cytoreduction treatment with steroids (up to 4 days) or hydroxyurea prior to and during the first cycle of treatment, and/or leukopheresis, to lower the WBC value to <15,000 cells/ μ L prior to Cycle 1, Day 1 dosing.

Note: Patients are not to receive treatment with study drug until their WBC value is $\leq 15,000 \text{ cells/}\mu\text{L}$.

If a Grade 2 or higher infusion-related hypersensitivity reaction is observed in 1 patient at any time during Part 1 of the study, all subsequent patients must receive prophylactic treatment (Section 5.2).

Concomitant steroid use is permitted as follows:

- Replacement doses of steroids for patients with adrenal insufficiency.
- Intranasal, inhaled, topical steroids, or local steroid injections (e.g., intra-articular injection).
- Intrathecal medication for CNS prophylaxis (not for active disease) per institutional standard of care practices.
- Prophylactic treatment with dexamethasone as follows may be instituted by the DESC based on emerging safety and PK profile:

ADCT-402-102 Protocol Amendment 3

o Dexamethasone 4 mg oral BID the day before investigational product (IP) administration, the day of IP administration, and the day after IP administration (Week 1/Day 1 of each cycle only, regardless of treatment schedule).

- o A 2-day course of dexamethasone 4 mg PO BID will be given (Week 1/Days 1 and 2 of each cycle). If possible, the first dose should be given at least 2 hours prior to IP administration. Any concomitant medication deemed necessary for the welfare of the patient during the study may be given at the discretion of the Investigator.
- Spironolactone, at standard doses, may be instituted at any time for patients with weight gain greater than 1 kg (2.2 lbs) from Cycle 1 Day 1, new or worsening edema and/or new or worsening pleural effusion. The dose of spironolactone may be titrated as clinically indicated. Additional diuretic support may be added if there is further increase in weight, edema or pleural effusion.

Any concomitant medication deemed necessary for the welfare of the patient during the study may be given at the discretion of the Investigator.

ADCT-402-102 Protocol Amendment 3

6 Study Assessments and Procedures

Patients will undergo the procedures at the time points specified in Section 4.1 and the Schedule of Procedures and Central Laboratory Sample Collection for the Q3W and QW dosing schedules (Table 5 through Table 9) in Appendix 12.1.

6.1 Efficacy Assessments

Assessment of response to treatment with ADCT-402 will be based on bone marrow samples (aspirate, or biopsy if aspirate unattainable). Bone marrow samples will be obtained as described in Section 4.1.2.1.

The activity of ADCT-402 will be evaluated based on the Investigator's evaluation of the patient's response to ADCT-402 as CR, CRi, PR, PD, or NR (Cheson, 2003; Döhner, 2010).

- Complete response is defined as achieving each of the following:
 - o Bone marrow differential showing $\leq 5\%$ blast cells,
 - Absolute neutrophil count $\ge 1.0 \times 10^9 / L$ and platelet count $\ge 100 \times 10^9 / L$,
 - o Absence of extra-medullary disease,
 - o Patient is independent of red blood cell (RBC) transfusions.
- Complete response with incomplete blood count recovery is defined as achieving all CR criteria except that values for ANC may be $<1.0 \times 10^9/L$ and/or values for platelets may be $<100 \times 10^9/L$.
- Partial response is defined as achieving each of the following:
 - o ANC $\geq 1.0 \times 109/L$ and platelet count $\geq 100 \times 109/L$,
 - O Bone marrow differential showing a \geq 50% decrease from baseline in the percentage of bone marrow blast cells to a level >5% and \leq 25%.
- No response is defined as not achieving CR, CRi, or PR.
- PD is defined as:
 - \circ For patients with CR or CRi, the first date of reappearance of blast cells in bone marrow and/or peripheral blood to a level ≥5%, or development of extramedullary disease.
 - o For patients with PR, the first date of an increase in blast cells in bone marrow and/or peripheral blood such that the patient does not continue to meet the criteria for PR.

As defined in Section 7.6.2, DOR and ORR will be defined among responders (CR, CRi, PR); OS and PFS will also be determined.

ADCT-402-102 Protocol Amendment 3

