- Partial response is defined as achieving each of the following:
 - ANC $\ge 1.0 \times 10^9$ /L and platelet count $\ge 100 \times 10^9$ /L.
 - Bone marrow differential showing a ≥50% decrease from baseline in the percentage of bone marrow blast cells to a level >5% and ≤25%,

bone marrow differential showing <5% blast cells.

- No response is defined as not achieving CR, CRi, or PR.
- PD is defined as:

ADCT-402-102 Protocol Amendment 3

o For patients with CR or CRi, the first date of reappearance of blast cells in bone marrow and/or peripheral blood to a level ≥5%, or development of extramedullary disease.

 For patients with PR, the first date of an increase in blast cells in bone marrow and/or peripheral blood such that the patient does not continue to meet the criteria for PR.

DOR and ORR will be defined among responders (CR, CRi, PR); OS and PFS will also be determined.

Safety Assessments: Safety will be assessed based on the evaluation of adverse events (AEs), serious AEs (SAEs), treatment discontinuations due to AEs, dose-limiting toxicities (DLTs), periodic 12-lead electrocardiogram (ECG) recordings, physical examinations, vital signs measurements, ECOG performance status, and hematology, coagulation panel, biochemistry, pregnancy (for women of child-bearing potential), and urinalysis test results obtained at various timepoints during the study. Adverse events will be graded according to CTCAE Version 4.0.

Definition of DLT:

A DLT is defined as any of the following events, except those that are clearly due to underlying disease or extraneous causes:

- A hematologic DLT is defined as:
 - Grade 3 or higher event of neutropenia or thrombocytopenia, or a Grade 4 anemia, with a hypocellular bone marrow lasting for 6 weeks or more after the start of a cycle, in the absence of residual leukemia (i.e., with

ADCT-402-102 Protocol Amendment 3

<5% blasts). In case of a normocellular bone marrow with <5% blasts, 8 weeks with \(\geq \) Grade 3 pancytopenia will be considered a DLT.

- A non-hematologic DLT is defined as:
 - o Grade 4 tumor lysis syndrome (Grade 3 TLS will not constitute DLT unless it leads to irreversible end-organ damage).
 - o Grade 3 or higher AE (including nausea, vomiting, diarrhea, and electrolyte imbalances lasting more than 48 hours despite optimal therapy; excluding all grades of alopecia).
 - CTCAE Grade 3 or higher hypersensitivity reaction (regardless of premedication).
 - o CTCAE Grade 3 or higher skin ulceration.

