4.1.2.1 Bone Marrow Sample

Within 6 days prior to Day 1 of Cycle 3, a bone marrow sample (aspirate or biopsy if aspirate unattainable) will be obtained for assessment of response to treatment and determination of MRD (via flow cytometry) by an approved clinical laboratory. Results must be available to the Investigator before the next dose of study drug is administered.

A bone marrow sample will then be obtained within 6 days prior to the Day 1 visit of Cycle 5 and at each subsequent cycle until CR or CRi (Section 6.1) is achieved or until disease progression. Once CR/CRi is achieved, sampling will be repeated at least every 3 cycles, or as clinically indicated.

A bone marrow sample will also be collected at the EOT visit (Section 4.1.8) for those patients who have not demonstrated disease progression and if their most recent sample was obtained more than $12 (\pm 1)$ weeks prior to the EOT visit.

Bone marrow aspirate sample collection with subsequent MNC isolation should follow the same collection schedule as above. Mononuclear cells from BMA will be used for retrospective central laboratory evaluation of CD19 and other CD markers (e.g., CD20, CD21, CD22).

ADCT-402-102 Protocol Amendment 3

Samples obtained during treatment and at the EOT visit are to be saved for biobanking (see Laboratory Manual). Additionally, when available, results from other analyses conducted as part of the institution's standard of care will also be collected.

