6.3.5.1 Hematology

The complete blood count (CBC) includes WBC with a 5-part differential, platelet count, hemoglobin, hematocrit, and ANC. Peripheral blasts will be included in the hematology analysis for Part 2 only. If the WBC value is <400 x 10⁶/L, a differential is not required. The coagulation panel must include partial thromboplastin time (PTT) and International Normalized Ratio (INR); prothrombin time (PT) expressed in seconds is optional. Patients taking coumarin-derivative anticoagulants should be monitored closely and their anticoagulant dose adjusted as needed.

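### Do the missing PD rule for never-responders and the two PR texts require a change to the plan?

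*Protocol*

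**What the plan says.** Protocol Section 6.1 leaves the response code (CR, CRi, PR, PD or NR) to the Investigator and cites two published sets of response recommendations. It then prints these rules:

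- **PD after CR or CRi:** "For patients with CR or CRi, the first date of reappearance of blast cells in bone marrow and/or peripheral blood to a level" of at least 5%, or new extramedullary disease.
- **PD after PR:** a rise in blasts that takes the patient outside the PR criteria.
- **NR:** "No response is defined as not achieving CR, CRi, or PR".
- **PR:** recovered ANC and platelets, plus a fall of at least 50%, worded "decrease from baseline in the percentage of bone marrow blast cells to a level >5% and" at most 25%.

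The synopsis repeats the PR rule and adds a line: "bone marrow differential showing <5% blast cells". The word joining that line to the one before it cannot be read in the text used here.

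On the data, Section 4.1.2.1 places the first post-baseline marrow as follows: "Within 6 days prior to Day 1 of Cycle 3, a bone marrow sample" is taken. Sampling resumes before Cycle 5 and then runs "at each subsequent cycle until CR or CRi (Section 6.1) is achieved or until disease progression". An end-of-treatment marrow is taken only "for those patients who have not demonstrated disease progression and if their most recent sample was obtained more than" 12 (±1) weeks before that visit. Section 6.3.5.1 says "Peripheral blasts will be included in the hematology analysis for Part 2 only".

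SAP 3.3 states that the trial ended before Part 1 was complete and that only Part 1 data will be analyzed. SAP 4.9 restricts efficacy to listings, with disease assessment shown as CR, CRi, PR, PD, NR or NE. SAP 4.1 defines only the Safety analysis set.

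**The concern.** The protocol relies on progression in patients who may never have responded. It is one route into the Efficacy analysis set (7.4), an event for PFS (7.6.2.4), a reason to stop treatment (4.2.1), and the end point of marrow sampling (4.1.2.1) and disease follow-up (3.1). Yet no printed rule turns rising blasts in a never-responder into PD. Taken literally, such a patient is NR and has no rule for dating progression. In a relapsed or refractory population this is not an exotic case. Two sites could code the same course differently.

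The PR discrepancy looks more serious because PR also has an operational use. Section 3.2 and the synopsis make extra patients at a lower dose level conditional on at least one PR, and going beyond 10 patients at a level conditional on at least 3 of the 10 reaching PR. If the two PR texts classify a patient differently, that condition could be read two ways. The listing in SAP 4.9 would also not show which text produced a given PR or NR.

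**Working it through.** There is no sample size, power or error rate behind this point, so there is no plan figure to reproduce. The check sets the rules side by side and then asks where the codes are used.

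**1. Never-responder with rising blasts.** Take an illustrative rise from 60% to 90%. CR and CRi need at most 5% blasts and PR at most 25%, so all three fail and the patient is NR. Both PD rules presuppose an earlier response, so neither applies. The result is the same under the synopsis. The gap in the printed criteria is real.

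**2. Two PR texts.** The extra synopsis line cannot be an additional requirement, since a marrow cannot be both above 5% and below 5%. It must be an alternative. Whether the count requirement still applies to it depends on the unreadable join. Illustrative baseline 40%, counts recovered, extramedullary disease present:

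| Marrow blasts | Section 6.1 | Synopsis |
|---|---|---|
| 4% | NR | PR |
| 6% (≤ 0.5 × 40% = 20%, and between 5% and 25%) | PR | PR |

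So under Section 6.1 the 4% patient ranks below the 6% patient, which suggests that a line was dropped.

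A grid shows where the texts part. It uses baseline 60%, nine blast values (0, 4, 5, 6, 20, 25, 30, 60, 90), and yes/no for recovered counts, extramedullary disease and transfusion independence: 9 × 2 × 2 × 2 = 72 states.

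- Narrow reading (counts must be recovered): 2 blast values below 5% × 3 ways of missing CR (extramedullary disease, transfusion dependence, or both) = 6 states, all NR in Section 6.1 and PR in the synopsis.
- Wide reading (the line stands apart from the count requirement): the same states with unrecovered counts also differ, 6 × 2 = 12.

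These are counts of constructed states, not patient frequencies.

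**3. Low baseline.** The Section 6.1 limb needs 0.5 × baseline > 5%, so baseline > 10%. The printed inclusion criteria give no minimum marrow percentage, but they rely on a WHO diagnosis that is not reproduced, so how often this arises is unknown.

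**4. Early data.** Cycle 3 Day 1 is nominal day 1 + 2 × 21 = 43, so the first scheduled marrow falls on days 37 to 42. Peripheral blasts are outside the Part 1 panel. Part 1 does have flow cytometry of peripheral white-cell populations with CD19 in Cycles 1 and 2 and at end of treatment (4.1.2, 4.1.8, 6.2.2), and available standard-of-care results (4.1.2.1). None of these is a scheduled blast count, but an Investigator is not without evidence.

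**5. Where the codes are used now.**

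- Efficacy analysis set, ORR, DOR and PFS: not carried into the SAP.
- SAP 4.9: a listing of assigned codes.
- Enrollment condition: permissive, applied during Part 1, and tied by Section 3.2 to the PR of Section 6.1.
- SAP 4.2: counts of discontinuation reasons, which are recorded by the Investigator and not derived from the PD rule.

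No step in the remaining analysis computes a response or a progression date from the printed criteria.

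**The case for a change.** The best case for a change is that this listing is the only efficacy output left, so its codes ought to be readable on their face. One footnote naming the PR text, the basis for PD in non-responders and the meaning of NE would cost little. Appealing to the cited publications does not close the gap: their titles concern acute myeloid leukemia, and the protocol does not say that they supply a PD rule for non-responders. Section 7.6.2.2 also drops the peripheral-blood criterion of Section 6.1, and neither document defines NE.

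The textual part of this stands. What does not follow is a change to the plan. A footnote naming the governing PR text would repeat the cross-reference in Section 3.2. One stating that PD is as judged by the Investigator would repeat Section 6.1. Giving the evidence behind each PD would mean going back to sites and would alter no code. Rewording the protocol needs a formal amendment (10.2.1) to a trial already stopped. The marrow-only wording in 7.6.2.2 matters only for a DOR that will not be estimated. NE may be defined in the CRF, which SAP Section 1 tells the reader to use alongside the SAP. The overlap at 5% (CR at or below, PD at or above) is narrower than it looks, because PD requires reappearance: a marrow of exactly 5% that establishes CR is not PD at that assessment.

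**Conclusion.** The printed PD criteria omit never-responders, and the two PR texts differ. The first is a gap that Investigator assessment fills; the second is most plausibly a clerical omission. Neither calls for a change. No planned estimate depends on either, no dose-escalation decision remains to be taken under the PR condition, and no recorded code would be revised. The possible misreading is confined to individual lines of one listing: a PD without an earlier response, or an NR in a patient below 5% blasts with extramedullary disease or transfusion dependence. The documents do not show that any such patient exists.

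This rests on three assumptions: efficacy stays listings-only as in SAP 4.9, codes are reported as the Investigators gave them, and Part 1 is not reopened. If ORR, DOR or PFS were to be estimated from these data, or the protocol were amended for another reason, the PR and PD passages would have to be reconciled first.

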6.2.1 Pharmacokinetic Assessments

The PK profile of ADCT-402 (total antibody; DAR \geq 0), PBD-conjugated antibody (DAR \geq 1), and free warhead SG3199 will be assessed by a central laboratory in Cycles 1 and 2. Additional PK and ADA samples will be collected, at the discretion of the Investigator, during any visit where toxicity is observed. A PK and ADA sample will also be collected concurrently with any other blood draw to assess safety (e.g., Unscheduled Visit), if possible. All PK samples will be evaluable as long as the actual collection times are recorded.

To understand the metabolic disposition of ADCT-402 in humans, samples remaining after PK analysis is complete may be pooled among patients for potential metabolite identification.

The PK profile will include determination of: maximum concentration (C_{max}), time to C_{max} (T_{max}), area under the concentration-time curve from time zero to the last quantifiable concentration (AUC_{0-last}), area under the concentration-time curve (AUC) from time zero to the end of the dosing interval ($AUC_{0-\tau}$), area under the concentration-time curve from time zero to infinity ($AUC_{0-\infty}$), accumulation index (AI), volume of distribution at steady-state (V_{ss}), mean residence time (MRT), terminal elimination phase rate constant (λz), terminal half-life ($T_{1/2}$), clearance (C_L), and volume of distribution (Vz).

6.2.2 Pharmacodynamic and Other Assessments

The following assessments will be performed at varying time points in the study:

- Flow cytometric assessment of CD19 and other CD marker expression in MNCs isolated from BMA and WB, tested retrospectively by a central laboratory in samples collected before treatment with ADCT-402.
- Level of ADAs against ADCT-402 in serum before, during, and after treatment with ADCT-402.
- Analysis of peripheral WBC populations and CD marker panel expression (e.g., CD19, CD20, CD21 and CD22) before, during, and after treatment with ADCT-402 (Cycles 1 and 2) by flow cytometry in WB.
- Serum concentrations of ADCT-402 and free warhead SG3199, QTc interval.
- Evaluation of MRD, by flow cytometry in bone marrow.

ADCT-402-102 Protocol Amendment 3

6.3 Safety and Tolerability Assessments

Safety will be assessed based on AEs, serious AEs (SAEs), treatment discontinuation due to AEs, DLTs, periodic 12-lead ECG recordings, physical examinations, vital signs measurements, ECOG performance status, and hematology, coagulation panel, biochemistry, pregnancy (for women of child-bearing potential), and urinalysis test results. Adverse events will be graded according to CTCAE Version 4.0. The Schedule of Events for the Q3W and QW dosing schedules are shown in Table 5 and Table 7, respectively, in Appendix 12.1.

